4.3 CLINICAL EXPERIENCE AND JUSTIFICATION OF PES LEVEL

The Phagenyx® System, or variants thereof, has been studied over a period of 15 years during development and more recent commercial studies in over 30 institutions in five countries. Most clinical studies have demonstrated that patients with dysphagia after stroke experience a clinical benefit associated with pharyngeal electrical stimulation when assessed using standardized measures of swallowing function and performance. Please see the Investigator's Brochure for complete information on these studies.

5 STUDY POPULATION

5.1 INCLUSION CRITERIA

CONFIDENTIAL Page 34 of 71

To be eligible to participate in this study, an individual must meet all of the following criteria:

- 1. Age \geq 18 and \leq 90 years.
- 2. Acute ischemic or hemorrhagic cerebral stroke within 7-28 days of baseline VFSS.
- 3. Score of 0 or 1 on NIHSS question 1a, Level of Consciousness.
- 4. *Moderate to severe dysphagia (PAS ≥4) on baseline VFSS (Baseline VFSS must meet the threshold criteria of demonstrating a PAS of ≥ 4, in three of the six boli (5 mL/1 tsp/bolus), during swallowing "thin liquid" barium media as assessed by the clinical staff administering the VFSS) unless its deemed too high risk then only 2 swallows will qualify.
- 5. Willing and able to have the Phagenyx® Catheter placed transnasally.
- 6. Willing and able to provide informed consent.
- 7. Stated willingness to comply with all study procedures and availability for the duration of the study.

*Note that the baseline VFSS will include testing with both thin liquids (up to 6 swallows) and nectar liquids (up to 6 swallows). For inclusion criterion 4, only the thin liquid swallows on the baseline VFSS will be considered. However, for descriptive statistics and other analyses, both the thin liquid and nectar liquid swallows on the VFSS will be considered.

5.2 EXCLUSION CRITERIA

An individual who meets any of the following criteria will be excluded from participation in this study:

- 1. Brainstem stroke.
- 2. Evidence of traumatic brain injury or subarachnoid hemorrhage.
- 3. Other, non-cerebrovascular, structural brain diseases, including multiple sclerosis or other demyelinating diseases, brain tumors (other than small meningioma), neurodegenerative diseases (including Alzheimer and Parkinson disease), hydrocephalus, and leukodystrophy
- 4. Dysphagia from conditions other than stroke.
- 5. Pre-stroke history of swallowing complaints or treatment or history of diseases known to be associated with swallowing problems (other neurological, head and neck cancer.
- 6. Distorted oropharyngeal anatomy (e.g., pharyngeal pouch, major pharyngeal surgery or head /neck surgery)
- 7. Currently being treatment for pneumonia.
- 8. Mute, global aphasia; no usable speech or auditory comprehension (scores 3 on NIHSS question 9, Best Language)
- 9. NIHSS score of 25
- 10. Presence of a tracheostomy
- 11. Any active implanted device (e.g., cochlear implant, ICD, permanent pacemaker)

CONFIDENTIAL Page 35 of 71

- 12. Any progressive neurological disorder (e.g., Parkinson's Disease, Multiple Sclerosis)
- 13. Cognitive impairment that prevents compliance with protocol-specific instructions and assessments
- 14. Unstable cardiopulmonary condition, i.e., not on maintenance therapy.
- 15. Currently participating in another investigational study
- 16. Pregnant or planning to become pregnant while participating in the clinical study
- 17. Known Allergy to oral radiographic contrast media (specifically barium)
- 18. Any other condition in the opinion of the investigator will prohibit the patient from participation and follow up.

5.3 SCREEN FAILURES

Screen failures are defined as patients who consent to participate in the clinical study but are not subsequently randomized to the study intervention or entered in the study. A record of screen failures, along with the reason for failure, will be kept in the database and/or on a Screening Log.

5.4 STRATEGIES FOR RECRUITMENT AND RETENTION

Patients will be screened and recruited by the investigators and/or coordinators at each site. Eligible patients could be in an inpatient rehabilitation center, having been transferred from the acute care facility in which they had been initially treated for the stroke, or site standard unit for post-acute stroke patients. The length of stay for these patients should be for up to 2 weeks to complete the study requirements for treatment and 14 day (+/- 1 day) follow up.

Stroke patients identified as dysphagic by clinical bedside assessments between the ages of 18 and 90 years, will be screened for study enrollment. The patient or their legal guardian will be eligible to sign the ICF after the study team explains the study and the patient and family have time to read and understand as well as ask all questions. The importance of study compliance will be emphasized throughout the informed consent process.

The length of study participation is approximately 11 weeks, including post treatment follow-up visits at 48 hours (+/- 24 hrs), 7 days (+/- 1 day), 14 days (+/- 1 day) or discharge, whichever is first, and 11 weeks (+/- 1 week).

6 STUDY INTERVENTION

6.1 STUDY INTERVENTION(S) ADMINISTRATION

CONFIDENTIAL Page 36 of 71

6.1.1 PHAGENYX® CATHETER PLACEMENT

[figure not shown]
All patients who have met screening and baseline criteria, signed an informed consent, and are enrolled in this study will require transnasal placement of the Phagenyx® Catheter which will remain in place for the minimum time required to complete three consecutive daily treatment sessions of active or sham stimulation. Patients will continue to receive nutrition via the same manner as prior to study entry, and will also have the Phagenyx® Catheter placed. Patients who already have an NGT will need to have it replaced with the Phagenyx® Catheter. Patients may receive feeding through the Phagenyx® Catheter as needed for up to 2 weeks in the US and up to 30 days in Europe.

The Phagenyx® Catheter should be configured to fit each patient optimally before it is inserted. This is done to ensure electrodes are in the correct position to deliver stimulation and the distal end of the Phagenyx® Catheter is in the proper position for the delivery of nutrition to the stomach, if being used for feeding. Numbers printed on the exterior of the Phagenyx® Catheter are indexed to align to the correct position in the pharynx based on patient measurements. See Instructions For Use (Phagenyx PNX-100 Catheter IFU) in the eTMF.

[figure not shown]
1. The distance from nostrils to earlobe to xiphisternum is measured out using the Phagenyx® Catheter with its distal tip positioned at the nostrils.

2. The number on the Phagenyx® Catheter printed guide is noted for correct Sleeve positioning so electrodes are properly placed in the pharynx.

[figure not shown]

3. The Sleeve is then adjusted so that the positioning guide is aligned over the number on the printed guide so that the heavy bars appear on either side of the number.

[figure not shown]

CONFIDENTIAL Page 37 of 71

[figure not shown]
4. The tube clamp on the Sleeve is closed to fix the relative positions of Sleeve and Phagenyx® Catheter components.

5. The Phagenyx® Catheter is inserted nasally using site standard technique, until the number below the positioning guide is at the patient's nostril. The position of the NGT is verified via standard institutional procedures to ensure the distal end is in the stomach via x-ray of catheter placement; auscultation of air in the stomach injected through the Catheter; and/or aspiration of stomach contents through the Catheter to confirm gastric pH, or per standard at each site.

6. The guidewire is removed and disposed of.

[figure not shown]
7. The Phagenyx® Catheter is secured in place as per standard practice for NGT placement (medical tape or custom bandage).

CONFIDENTIAL Page 38 of 71

8. The Garment clip is attached to the patient and proximal end of the Phagenyx® Catheter inserted into the tube grip for comfort.

If the Phagenyx® Catheter will also be used for feeding, the enteral connector is connected to a suitable enteral feeding set (use of the supplied adaptor, as needed). Prior to NGT feeding, the correct placement of the NGT should be verified to avoid feeding into any space other than the stomach.

6.1.2 VITAL SIGNS MONITORING

Vital signs monitoring is required for approximately the first 20 patients receiving active treatment (including roll-in patients). To maintain the blind, the vital signs will be obtained on all patients including those randomized to sham treatment, until there are data for 20 patients who have received active treatment; this applies to all three days of treatment. Vital signs monitoring includes blood pressure, heart rate, and ECG monitoring. Immediately (within 5 minutes) prior to beginning PES treatment, the user will obtain and record pre-treatment blood pressure and heart rate numbers, as well as a 30-second ECG rhythm strip. Vital signs monitoring will continue throughout the duration of study treatment and any significant changes (i.e. noticeable increases) will be documented for study records. A second ECG rhythm strip is required 5 minutes into the PES treatment, and a third ECG rhythm strip is required immediately (within 5 minutes) post treatment. Immediate post-treatment blood pressure and heart rate numbers will again be obtained and recorded.

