1.2 SCHEMA

1.3 SCHEDULE OF ACTIVITIES (SOA)

	Screening	Baseline	Phagenyx Treatment (10 minutes per day, 3 consecutive days)	48±24 Hour Follow- up	7±1 Days Follow -up	14-±1 days or discharge, whichever is first	11±1 Weeks Follow -up
				Follow-up ti	iming is base	ed on last Phageny	x treatment.
Medical History and Demographics	Х						
Exam of nasopharynx		X ¹			X ¹	X	
Informed Consent	Х						
ECG monitoring (for the first 20 patients randomized to active treatment)			X ²				
Heart Rate and Blood Pressure Monitoring(for the first 20 patients randomized to active treatment)			X ²				
NIHSS		Х				X	Х
Modified Rankin Score (mRS)		X				Х	Х
Barthel Index		Х				Х	Х
FOIS		Х			Х	Х	Х
DSRS		Х			Х	Х	Х
EQ-5D, EQ-VAS		X					Х
Pregnancy Test		X3					

CONFIDENTIAL Page 13 of 71

VFSS	X ⁴		Х			
Pneumonia Assessment	Χ		Χ	X	X	
Adverse Event (AE) Assessment	X	Х	Х	X	Х	X
Blinding Assessment					X	

¹ Assessment of nasopharynx at baseline, 1 week after catheter is in place and at catheter removal using flashlight or pen light. In the event of patient complaint or obvious symotoms, a fiberoptic exam is required and any adverse events are to be reported.

CONFIDENTIAL Page 14 of 71

² Rhythm strip (30 seconds) printed at immediately prior to commencing PES treatment, 5 minutes into each of the three treatment sessions, and immediately post treatment. Continual ECG monitoring during PES to observe for any arrhythmias. Heart rate and Blood Pressure to be documented immediately prior to and after PES.

³ Required only for females of child-bearing potential

⁴ Baseline VFSS must meet the threshold criteria of demonstrating a PAS of ≥ 4, in three of the six boli (5 mL/1 tsp/bolus), during swallowing "thin liquid" barium media as assessed by the clinical staff administering the VFSS, unless its considered to be too high risk, then 2 swallows will qualify.

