A core laboratory will be established for analysis of all procedural VFSS. The VFSS core lab will provide standardized baseline and follow-up analyses of the primary endpoint as well as VFSS-related tertiary endpoints. Personnel at the VFSS core lab will also be blinded to patient treatment assignment.

Up to three unblinded, active treatment roll-in patients will first be enrolled at each site in the US. The need for roll-in patients for European sites will be based on experience with the CE-marked device at the site and will be agreed to by Phagenesis and the site investigator. Roll-in patients will enable the site study staff to become fully proficient in the most effective way to administer the Phagenyx® treatment as well as perform other protocol-specific assessments. The sponsor will provide detailed training and education to the site staff in the use of the Phagenyx system and the protocol. The sponsor will provide an on-site representative to oversee and provide aid in the administration of PES during treatment of these roll-in patients. The sponsor will complete the Site Training and Competency Review form during the visit(s). The site will be approved to begin randomizing patients after the site meets the following competency requirements:

- The treatment administrator successfully and confidently completes up to three treatment sessions with little to no prompting or other aid from the sponsor representative,
- The treatment parameters recorded on the Base Station reflect appropriate stimulation levels, and
- Electronic case report forms (eCRFs) for baseline through the acute follow-up visit are completed correctly within 5 days of enrollment then within 5 days of each follow up for the roll-in patients.

CONFIDENTIAL Page 33 of 71

A formal review of site competency will be made after one to three roll-in patients have been treated, and the site is competent based on the above parameters. The site investigator and other relevant personnel will meet with sponsor personnel or their designee(s) via teleconference or on site to review the roll-in patient records and answer outstanding questions. The sponsor or their designee will provide approval to begin randomizing patients by controlling access to the randomization module of the study's EDC system. Meeting documentation including recommended actions and decisions will be retained in the eTMF for each site.

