2.5. Study Procedures

The schedule of assessments, as outlined in the study protocol, is provided in **Error! Reference source not found.**

 Table 1
 Schedule of Assessments

	Screening	Baseline	Phagenyx Treatment (10 minutes per day, 3 consecutive days)	48±24 Hour Follow- up	7±1 Days Follow- up	14-±1 days or discharge, whichever is first	11±1 Weeks Follow- up	
				Follow-up timing is based on last Phagenyx treatment.				
Medical History and Demographics	Х							
Exam of nasopharynx		X ¹			X ¹	X		
Informed Consent	Х							
ECG monitoring (for the first 20 patients randomized to active treatment)			X ²					
Heart Rate and Blood Pressure Monitoring(for the first 20 patients randomized to active treatment)			X ²					
NIHSS		Х				Х	Х	
Modified Rankin Score (mRS)		Х				Х	Х	
Barthel Index		Х				Х	Х	
FOIS		Х			Х	Х	Х	
DSRS		Х			Х	X	Х	
EQ-5D, EQ-VAS		Х					Х	
Pregnancy Test		X ³						

VFSS	X ⁴		X			
Pneumonia Assessment	X		Х	Χ	X	
Adverse Event (AE) Assessment	Х	Х	X	Х	Х	X
Blinding Assessment					Х	

¹ Assessment of nasopharynx at baseline, 1 week after catheter is in place and at catheter removal using flashlight or pen light. In the event of patient complaint or obvious symotoms, a fiberoptic exam is required and any adverse events are to be reported.

² Rhythm strip (30 seconds) printed at immediately prior to commencing PES treatment, 5 minutes into each of the three treatment sessions, and immediately post treatment. Continual ECG monitoring during PES to observe for any arrhythmias. Heart rate and Blood Pressure to be documented immediately prior to and after PES.

³ Required only for females of child-bearing potential

⁴ Baseline VFSS must meet the threshold criteria of demonstrating a PAS of ≥ 4, in three of the six boli (5 mL/1 tsp/bolus), during swallowing "thin liquid" barium media as assessed by the clinical staff administering the VFSS, unless its considered to be too high risk, then 2 swallows will qualify.

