3. SUBJECT POPULATIONS

3.1. Population Definitions

The following subject populations will be evaluated and used for presentation and analysis of the data:

- The Roll-In (RI) population will consist of all patients enrolled in a non-blinded roll-in manner and remained eligible to receive the Phagenyx treatment after initial pre-procedural VFSS testing is completed and the PAS is determined to meet entry criterion and no exclusions are found. All patients in whom treatment was attempted, regardless of procedural outcome, will be included in this analysis set.
- The **Safety Population** will consist of all patients that were enrolled in the study (including Roll-In patients) and underwent the pre-procedural VFSS with or without subsequent placement of the Phagenyx Catheter.
- The **Intent to Treat (ITT)** Population will consist of all patients that were randomized, irrespective of their protocol adherence and continued participation in the study.
- The **Per Protocol (PP) Population** will consist of all randomized patients who completed the full Phagenyx treatment regimen according to their randomization assignment and for whom completed primary endpoint data are also complete.

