4.3. General Statistical Methods and Data Handling

4.3.1. General Methods

All output will be incorporated into Microsoft Excel or Word files, sorted and labeled according to the International Conference on Harmonisation (ICH) recommendations, and formatted to the appropriate page size(s).

Tabulations will be produced for appropriate demographic, baseline, efficacy and safety parameters. For categorical variables, summary tabulations of the number and percentage within each category (with a category for missing data) of the parameter will be presented. For continuous variables, the mean, median, standard deviation, minimum and maximum values will be presented. Time to event data will be summarized using Kaplan-Meier Methodology using 25th, 50th (median), and 75th percentiles with associated 2-sided 95% confidence intervals, as well as percent of censored observations.

Formal statistical hypothesis testing will be performed on the primary and secondary efficacy endpoints with all tests conducted at the 1-sided, 0.025 level of significance. Summary statistics will be presented, as well as confidence intervals on selected parameters, as described in the sections below.

For all analyses, baseline will be defined as the most recent measurement prior to the date and time of the administration of active treatment with Pharyngeal Electrical Stimulation or a sham treatment. Therefore, baseline may be on the same day as the start of study treatment, but prior to the administration of the study treatment.

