4.9. Safety Analyses

Safety analyses will be conducted using the Safety Population.

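### Protocol 6.1.2 and the two schedules count the roughly 20 cardiac-monitored patients differently, and the SAP's summary rules leave the on-stimulation ECG strips out of the tables

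*Protocol*

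**What the plan says.** **Who is monitored.** Protocol 6.1.2 reads: "Vital signs monitoring is required for approximately the first 20 patients receiving active treatment (including roll-in patients"). It also covers the sham arm until 20 active-treated patients have data: "To maintain the blind, the vital signs will be obtained on all patients including those randomized to sham treatment". The schedule in Protocol 1.3 describes the cohort as "ECG monitoring (for the first 20 patients randomized to active treatment"). Its heart-rate and blood-pressure row uses the same count, and SAP Table 1 repeats both rows. Roll-ins are not randomized. Protocol 4.1 says: "Up to three unblinded, active treatment roll-in patients will first be enrolled at each site in the US".

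**What is recorded.** Each of three daily sessions has a rhythm strip before stimulation, then "5 minutes into each of the three treatment sessions, and immediately post treatment" (schedule footnote 2). Heart rate and blood pressure are documented before and after each session.

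**How it is summarized.** SAP 4.3.9 summarizes by scheduled visit and, where a visit has several assessments, uses the last. SAP 4.9.4 tabulates normal and abnormal ECG results at baseline and at each study visit, and lists all ECG data. SAP 4.9.3 summarizes vital signs as values and changes from baseline at each on-study evaluation. In SAP 4.3.1, "baseline will be defined as the most recent measurement prior to the date and time of the administration of active treatment" or sham, and the next sentence ties this to the start of study treatment.

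**Which patients.** SAP 4.9 states: "Safety analyses will be conducted using the Safety Population". SAP 3.1 defines that population as "all patients that were enrolled in the study (including Roll-In patients) and underwent the pre-procedural VFSS". SAP 4.9.3 and 4.9.4 do not say whether roll-ins are shown apart from randomized active patients.

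**The concern.** Two separate matters arise.

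First, a site working from 6.1.2 and a site working from the schedule would reach different minimum stopping points. Roll-ins come first at US sites, so the choice of count affects how many monitored active patients are randomized and how many concurrent sham patients are monitored alongside them.

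Second, the strip taken 5 minutes into stimulation is the reading that bears most directly on whether the stimulation disturbs cardiac rhythm. The protocol requires it, yet the SAP's general rules give it no place in a table. For heart rate and blood pressure, a change at session 2 or 3 measured from before session 1 mixes day-to-day drift with the effect of that session, although a fresh pre-session reading exists each day. What is at stake is the clarity of the cardiac safety summaries in a submission package.

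**Working it through.** The plan states no figure for this point, so there is none to reproduce. The check sets the texts side by side and applies the SAP's rules to the scheduled readings.

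**1. The count.** Inputs: about 20 active patients with roll-ins counted (Protocol 6.1.2); 20 randomized active patients (Protocol 1.3, SAP Table 1); up to three roll-ins per US site (Protocol 4.1). Let r be the number of roll-ins among the 20 under 6.1.2.

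- Randomized active patients monitored under 6.1.2 = 20 − r. For r = 0, 5, 10, 15, 20 this gives 20, 15, 10, 5, 0.
- Randomized active patients monitored under the schedules = 20, whatever r is.
- Concurrent sham patients are about equal in number to the randomized active patients if allocation is 1:1. The documents do not state the ratio, so this is an assumption.
- Seven US sites with three roll-ins each give 7 × 3 = 21, enough to fill the 20 under 6.1.2 with no randomized patient.

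At least about 20 active patients are monitored on either count. With zero events in 20, the one-sided 95% upper bound is 1 − 0.05^(1/20) = 13.9%.

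A simulation illustrates the likely mix. It assumed 15 sites, 9 or 12 of them in the US; 225 patients in 24 months; sites opening over 0 to 12 months; one to three roll-ins at US sites only; and 1:1 allocation. Scenario means under 6.1.2 were 6.0 to 17.2 roll-ins and 2.7 to 14.0 sham patients. These ranges are not bounds. Protocol 4.1 also allows European roll-ins. Giving European sites three roll-ins each as well, with all sites open at once, lowers mean sham to about 0.4.

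**2. The ECG strips.** Scheduled strips per patient = 3 sessions × 3 time points = 9, of which 3 are on stimulation. Apply SAP 4.3.1 (baseline), 4.3.9 (last of a visit) and 4.9.4 (baseline and visits):

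- Each session is a visit: session-1 pre-treatment strip + three post-treatment strips = 1 + 3 = 4 of 9.
- The treatment column is one visit: session-1 pre-treatment strip + session-3 post-treatment strip = 1 + 1 = 2 of 9.
- On-stimulation strips tabulated: 0 of 3 either way, because a post-treatment strip follows. The exception is a missing post-treatment strip, which can leave the 5-minute strip as the last one.
- Strips listed: 9 of 9.

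For 20 patients that is 180 strips, of which 80 or 40 are tabulated. None of the 60 on-stimulation strips is tabulated when post-treatment strips are complete.

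**3. The vital-sign baseline.** SAP 4.3.1 does not say first administration, but its reference to the start of study treatment points to one reading before session 1. SAP 4.9.3 then measures change from that reading. Neither document plans a pre-to-post change within a session.

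**The case against.** The strongest reply is that little depends on this. SAP Table 1 reproduces the protocol's schedule, so it is a copy and not a second independent source. Either count gives at least about 20 active patients. Sham readings are taken to protect the blind, and no active-versus-sham cardiac contrast is planned. Continual ECG observation, documentation of significant changes, adverse event tables and full listings all remain. This stands, and it is why the priority is minor.

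Four stronger readings are tempting and are not supported:

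- *Sites cannot comply with both texts.* They can. Protocol 6.1.2 sets a minimum and forbids no further monitoring, so continuing until 20 randomized active patients have data satisfies both.
- *ECGs at sessions 2 and 3 are tested against session 1.* SAP 4.9.4 plans no ECG change from baseline, only result categories side by side. If the treatment column is one visit, session 2 is not tabulated at all.
- *Vital-sign drift is necessarily mixed with the session effect.* The reference in SAP 4.9.3 to each on-study evaluation may already cover the pre-session readings on days 2 and 3. Drift would then be visible in its own row, though a within-session change would still not be planned.
- *Roll-ins will be pooled unseen with randomized patients.* Protocol 4.1 and SAP 2.1 analyze roll-ins independently of the primary analysis population, and SAP 4.7 summarizes their baseline data as a population. This does not settle the ECG and vital-sign tables, which use the Safety Population.

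It is also fair to say that the rule in SAP 4.3.9 is a general one and may not have been written with within-session strips in mind. But it is the stated rule, and nothing exempts these readings from it.

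**Conclusion.** The difference in counts is explicit in the text and needs no assumption. Its practical size depends on roll-in numbers, site mix and allocation ratio, which the documents do not fix, so the simulated counts are illustrations only.

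The omission of the on-stimulation strips follows from applying SAP 4.3.9 together with 4.9.4. It holds under both meanings of a visit, provided the post-treatment strip is present. The vital-sign point is weaker: a single pre-session-1 baseline is the most natural reading and not the only one, while the absence of a planned within-session change is plain.

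A reader might infer that rhythm data are lost or that cardiac events could go unreported. The documents do not support that, because everything is listed and arrhythmias remain subject to observation and adverse event reporting. The gap is in the planned safety summaries. Minor priority.

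**What to change.** - **Count.** Change the ECG row and the heart-rate/blood-pressure row in Protocol 1.3 and SAP Table 1 to match Protocol 6.1.2. That is two row labels in each document, and it adds no monitoring beyond what 6.1.2 already requires. The randomized-only count would also be coherent and would give more concurrent sham readings, but it monitors more patients.
- **Summaries.** In SAP 4.9.3 and 4.9.4, exempt treatment-session readings from the last-assessment rule in SAP 4.3.9. Summarize them descriptively by arm, session and time point: before, at 5 minutes and after for ECG; before and after for heart rate and blood pressure. Set each against that session's own pre-treatment reading.
- **Roll-ins.** Show them separately from randomized active patients in these tables.

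The cost is a few extra descriptive tables built from readings already collected. No hypothesis test is added, and the primary analysis does not change.
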